**Title: Bubble PEP Training Among Patient
With Chronic Obstructive Pulmonary
Disease in Pulmonary Function Effects**

Study Protocol

Principal Investigator : [name]
ClinicalTrials.gov number: NCT04828837

2021/02/25

Material and Methods

Design and Participants

A randomized controlled trial with a single-blind study design was conducted. Using convenience sampling, data were collected from February 2021 to July 2021 at two teaching hospitals in northern Taiwan. Random serial numbers were generated by a research assistant using Random Allocation Software. The research assistant then put each serial number into an opaque envelope. After agreeing to participate in this study, each participant received an envelope and opened it to find out whether they belonged to the experimental group or the control group. The research assistant who assisted with recruitment did not engage in data collection or analysis.

The inclusion criteria were patients who diagnosed AECOPD and were 40 years old or older, conscious, could read articles, agreed to participate in the study, and signed an informed consent document. Exclusion criteria included patients who had used non-invasive PEP treatment before or during hospitalization, who had a mental disorder. The G*Power 3.1.9.7. software was used to estimate the sample size. A sample size of at least 26 has 80% power to detect the largest effect size of 0.5. An alpha level of 0.05 was used.

Measurements

The participants' demographics and clinical characteristics were collected, including gender, age, marital status, occupation, smoking history, chronic comorbidities (hypertension, diabetes mellitus, heart disease, lung cancer, and pneumothorax), COPD stage and dry powder bronchodilator use.

Chinese Version of the CAT

A total of eight items were used to assess the degree of dyspnea of the patients. Each item had a score ranging from 0 to 5 points, with the highest total score being 40

points. The higher the score, the higher the degree of dyspnea (Pothirat et al., 2015). The present study Cronbach's α was 0.88, and the Intraclass Correlation Coefficient (ICC) was 0.8.

CSSAQ

The CSSAQ was used to assess patients' cough and sputum symptoms. The content of the questionnaire was prepared with reference to published literature. The questionnaire consisted of 25 questions, including questions related to cough, sputum, and psychological symptoms and effects, on a four-point Likert scale with scores ranging from 0 to 4. The higher the score, the worse the cough or sputum symptoms (French et al., 2002). The index of content validity was 1, while Cronbach's α was 0.97.

PEFR

The patients' pulmonary ventilation was assessed using the TruZone peak flow meter. This device was also used to monitor FEV1. Several studies showed good internal consistency of this measurement instrument, with a Cronbach's α of 0.99 (Folgering et al., 1998; Martinez et al., 2017). In this study, Cronbach's α was 0.97.

Bubble PEP bottle

The bubble PEP device consisted of a 500cc water bottle and a short tube that was 0.8 cm in diameter and 45 cm in length. The tube was inserted into the water bottle, and 10 cm of the tube was placed underwater to form a breathing training water bottle with a positive pressure of 10 cmH₂O.

Bubble PEP training

The patients trained three times a day with a bubble PEP bottle, and each training session lasted 20 minutes. During the training session, each patient maintained a 90-degree sitting posture. After taking a deep inhalation, each patient held the bottle and blew air out through the tube into the water. The ratio of inhalation to blowing was 1 to

3 seconds. The patient rested for at least 1 minute after each bout of inhalation and blowing. After completing 10 blows, the patients exhaled 3 times, took deep breaths, and coughed. The breathing training continued for 30 days. The participants were advised to avoid training one hour before and two hours after meals.

Procedures

After the experimental and control groups agreed to participate in this study and completed the consent forms, the two groups took pre-tests, which measured the Chinese version of the CAT, the CSSAQ, and the PEFR, within 48 hours of hospitalization, which served as the baseline of the intervention (T0). Data were collected again on the 7th day (T1) and the 30th day (T2) of the intervention to evaluate the effect of the intervention on pulmonary function. Only the experimental group received bubble PEP training, while the control group had routine medical care. If participants were discharged from the hospital in the middle of the study, the investigator monitored the intervention effectiveness via weekly follow-up telephone calls.

The study procedures are shown in Figure 1. Of the 57 patients who met the criteria were invited to participate for study eligibility. 14 of the remaining 27 participants, 13 and 14 were assigned to the intervention and control groups, respectively. 7days follow-up (T1) data were obtained for 17 of the participants. 1M follow-up (T2) analyses were performed among the 14 participants with complete data. The attrition rates were 30% and 71% for the experimental and control groups, respectively, with an overall attrition rate of 52%.

Ethical considerations

The study protocol was reviewed and approved by the Institutional Review Boards of Fu Jen Catholic University Hospital and En Chu Kong Hospital (FJUH109078 & ECKIRB1091006). Participants were required to sign informed consent forms before

the study and were allowed to terminate or withdraw from the study at any time. Data collected from the participants were coded, de-identified, and kept in a locked cabinet (ClinicalTrials.gov number: NCT04828837).

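### Nothing in the visible text requires T0 to be completed before the patient opens the allocation envelope; read in sequence, the baseline is taken with the arm known

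*Protocol*

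**What the plan says.** Under Design and Participants, allocation is by opaque envelope, and the patient learns the arm personally: "After agreeing to participate in this study, each participant received an envelope and opened it". Agreement is the only step placed before the opening.

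Under Procedures, the baseline is described separately: "After the experimental and control groups agreed to participate in this study and completed the consent forms, the two groups took pre-tests". These are the measurements "which measured the Chinese version of the CAT, the CSSAQ, and the PEFR", taken within 48 hours of hospitalization and designated T0. The same section refers to Figure 1 for the study procedures; that figure is not available in the text.

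On blinding, Design and Participants says "A randomized controlled trial with a single-blind study design was conducted" and does not say who is blinded. The assistant who helped with recruitment took no part in data collection or analysis. On the comparator, Procedures says "Only the experimental group received bubble PEP training, while the control group had routine medical care".

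The SAP evaluates the intervention effect by GEE. It does not say whether T0 enters as a repeated outcome or as a covariate.

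**The concern.** A baseline in a randomised trial should be recorded before anyone who can influence it knows the allocation. Here the person with most influence is the patient, who answers the CAT and CSSAQ and supplies the effort for the PEFR. With no sham, opening the envelope tells the patient whether training will follow.

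If T0 comes after the opening, knowledge of the arm can alter the answers or the effort. A patient pleased or disappointed by the allocation may score symptoms higher or lower, or blow harder or less hard, so the direction cannot be predicted. T0 would then no longer be a pre-allocation measurement. A difference between arms at T0 could not be put down to chance alone, and T0 would not be a safe adjustment covariate. With 27 patients assigned, even a modest distortion counts.

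**Working it through.** **Step 1. The order in the text.**

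| Step | Where | What it is placed after |
|---|---|---|
| Envelope opened by patient | Protocol, Design and Participants | Agreement to participate |
| T0: CAT, CSSAQ, PEFR | Protocol, Procedures | Agreement and completed consent forms |

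Two sequences fit:
- (a) consent, envelope, T0;
- (b) consent, T0, envelope.

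Sequence (a) is the more natural: agreement is the only step before the opening, and a site following that sentence literally would hand over the envelope at once. Sequence (b) is not excluded, and no visible sentence requires it.

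**Step 2. Does anything else protect T0?**
- Control condition: routine care without a sham, so an opened envelope reveals the arm.
- Single-blind design: the blinded party is not named, and after opening it cannot be the patient.
- Separate recruiting assistant: this keeps the recruiter away from the measurements but does not keep the patient unaware of the arm.

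None of these protects T0 under sequence (a).

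**Step 3. What a shift would do.** The plan gives no figure to reproduce. Let b be an arm-dependent shift at T0 and p the fraction of it still present at T1 or T2. With no true effect:

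bias in the change contrast = pb − b = −(1 − p)b

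Only the non-persistent part, δ = (1 − p)b, matters for the change. If T0 were a covariate with slope β and p = 0, the bias would be −βb. With equal SDs and correlation 0.5, β = 0.5 and the bias is half as large.

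**Step 4. Illustrative size.** Inputs from Procedures: 13 and 14 patients assigned. From the SAP: two-sided 5% level. Assumed, because the documents do not give them: the shift, and a correlation ρ = 0.5 between T0 and follow-up. A two-sample t-test on change stands in for the GEE.

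- Change-score SD = σ√(2(1 − ρ)) = σ√(2 × 0.5) = σ
- Noncentrality = δ/σ × √(13 × 14 / 27) = δ/σ × 2.596
- Degrees of freedom 25; critical value 2.060

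| Non-persistent shift (SD) | Noncentrality | False-positive rate |
|---|---|---|
| 0 | 0 | 5.0% |
| 0.1 | 0.260 | 5.7% |
| 0.2 | 0.519 | 7.9% |
| 0.3 | 0.779 | 11.6% |
| 0.5 | 1.298 | 23.9% |

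**Step 5. Sensitivity to attrition.** Procedures reports attrition of 30% and 71%. Taking 4 of 13 and 10 of 14 as lost leaves 9 and 4. That makes 13, whereas the text reports 14 with complete data, so this split is only a reading of the percentages. The multiplier becomes √(9 × 4 / 13) = 1.664 with 11 degrees of freedom. Shifts of 0.2, 0.3 and 0.5 SD then give 6.1%, 7.4% and 11.9%. The bias in the estimate is unchanged; the rates are lower only because the smaller sample has less power to detect anything.

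**The case against.** The strongest reply is that the order is simply unstated. A reader might infer that patients did open the envelope before T0, particularly because Procedures speaks of two groups taking the pre-tests. That wording does not establish it: the same sentence applies the group names to patients at the moment of agreeing, before any envelope could be opened, so they are retrospective labels. Figure 1 may also show the order, and its absence from the text cannot be held against the plan. All of this stands, and the point is therefore limited to what the visible text fails to require.

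A reader might also infer that any shift at T0 carries over in full to the treatment effect. It need not. Patients know their arm at T1 and T2 under either order, so whatever part of the shift persists cancels in the change from T0. If T0 is a covariate, the slope scales the shift. The SAP does not say which applies.

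A third tempting inference is that disappointed control patients left between the envelope and T0. Procedures reports heavier attrition in controls, but the losses it describes are at the 7-day and 30-day follow-ups. It reports no departure before T0.

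Finally, the protocol is in the past tense and already reports attrition, so the sequence cannot be changed for patients already measured. That is right, and it restricts the remedy for them to disclosure. It does not remove the point: the sequence determines whether T0 is a pre-allocation baseline, and the visible text leaves it open.

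**Conclusion.** The point holds in conditional form. The visible text does not require T0 to be completed before the envelope is opened, and nothing else described would keep the patient unaware of the arm if it is not. The order actually used is unknown.

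If T0 followed the opening, the group-by-time contrast is exposed to bias of unknown size and direction. The range of 5.7% to 23.9% for non-persistent shifts of 0.1 to 0.5 SD is an illustration. It rests on an assumed shift, an assumed correlation of 0.5, all 27 patients analysed, and a t-test in place of the GEE. It shows how sensitive a trial of this size would be, and it does not estimate what happened here.

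The change should be made: it is specific, costs almost nothing, and protects the measurement from which change is judged.

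**What to change.** In the protocol, under both Design and Participants and Procedures, set one sequence:
1. Consent signed.
2. T0 (CAT, CSSAQ, PEFR) completed and recorded.
3. Envelope handed over and opened.

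State in the same place who is blinded.

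For data already collected, report the order actually used. Dated T0 forms and envelope-opening records, if kept, would settle it. If T0 followed the opening, describe T0 as a post-allocation measurement wherever baseline comparisons or changes from T0 are reported. If the order differed between patients or cannot be established, say so.

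Cost: for any further recruitment, only the order of two existing steps changes, with no added visits or staff. For completed data, the cost is a check of records, if kept, and a few sentences of reporting.

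### With no primary outcome and one .05 rule, a symptom score from patients who know their arm can be reported as the intervention effect in a trial about pulmonary function

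*Protocol*

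**What the plan says.** Protocol, Design and Participants: "A randomized controlled trial with a single-blind study design was conducted". The blinded party is not named. After consent, "each participant received an envelope and opened it to find out whether they belonged to the experimental group or the control group". The only stated separation of roles is that the recruiting assistant took no part in data collection or analysis.

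Protocol, Procedures: "Only the experimental group received bubble PEP training, while the control group had routine medical care". No sham device is described. CAT, CSSAQ and PEFR are listed for T0. Data are collected again at day 7 (T1) and day 30 (T2), "to evaluate the effect of the intervention on pulmonary function".

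Protocol, Measurements, describes the instruments as follows:
- CAT: "A total of eight items were used to assess the degree of dyspnea of the patients".
- CSSAQ: "The higher the score, the worse the cough or sputum symptoms".
- PEFR: "pulmonary ventilation was assessed using the TruZone peak flow meter". The next sentence adds that the same device monitored FEV1, which does not appear in the Procedures list.

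The sample size statement, "A sample size of at least 26 has 80% power to detect the largest effect size of 0.5", names no outcome, time point, test or effect-size index. The SAP says that the intervention effect was evaluated by GEE, with two-tailed tests and significance at p below .05. It gives no outcome hierarchy and no multiplicity rule.

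**The concern.** Three features combine. Patients know whether they trained. Two of the three listed outcomes are their own ratings of dyspnea, cough and sputum, so blinding an assessor or analyst would not protect those answers. No rule says which outcome decides the trial.

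The stated target is pulmonary function. Of the three listed tests, PEFR is the one that the protocol describes in those terms. Followed as written, the SAP lets a significant CAT or CSSAQ result carry the conclusion even if PEFR shows nothing. That conclusion would then rest on the measures most open to expectation, and it would be picked from several tests that each used the full .05.

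**Working it through.** **Count of contrasts.** The documents do not list the contrasts, so the count is inferred.

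| Reading of the plan | Questionnaire tests | All tests |
|---|---|---|
| 3 listed outcomes, each compared at T1 and T2 | 2 × 2 = 4 | 3 × 2 = 6 |
| One joint group-by-time test per listed outcome | 2 | 3 |
| FEV1 also analysed, each compared at T1 and T2 | 2 × 2 = 4 | 4 × 2 = 8 |

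The first reading fits the Procedures list best. Questionnaires make up two thirds of the tests under the first two readings and half under the third.

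**False positives with no true effect and no reporting bias.** Each test is two-sided at .05 (SAP). For k independent tests, P(at least one) = 1 − 0.95^k:
- k = 6: 1 − 0.735 = 26.5%
- k = 4 (questionnaires only): 18.5%
- k = 3: 14.3%
- k = 2 (PEFR at T1 and T2): 9.75%

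Contrasts within one trial are likely to be correlated. For a common correlation ρ (assumed) and normal test statistics, P = 1 − ∫ φ(z) [Φ((1.96 − √ρ z)/√(1−ρ)) − Φ((−1.96 − √ρ z)/√(1−ρ))]^k dz:

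| ρ | 6 contrasts | 2 PEFR contrasts |
|---|---|---|
| 0 | 26.5% | 9.75% |
| 0.3 | 24% | 9.5% |
| 0.5 | 21% | 9% |
| 0.7 | 16% | 8% |
| 0.8 | 14% | 8% |

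The range for six tests is therefore about 14% to 26%, against 5% for one. Two PEFR contrasts, each at .05, still run at about 8% to 10%. Moving to PEFR without a further rule is not enough.

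**Sensitivity to reporting bias (illustration only).** The documents give no size for such a bias. Suppose that knowing the arm shifts one questionnaire difference in change by δ SD in favour of training, and that all 13 and 14 allocated patients are counted (Procedures; ITT with EM in the SAP). Then SE = √(1/13 + 1/14) = 0.385 SD. The smallest significant difference is t(25, .975) × SE = 2.060 × 0.385 = 0.793 SD. The noncentral t with noncentrality δ/0.385 gives the chance of a significant result in favour of training: 2.5% at δ = 0, 4.4% at 0.1, 9.1% at 0.25 and 23.8% at 0.5. With only the completers implied by 30% and 71% attrition (9 v 4), SE = √(1/9 + 1/4) = 0.601 SD, and the chance is 5.7% at 0.25 and 11.5% at 0.5. The bias can only add to the multiplicity figures, but its amount is unknown and may be zero.

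**Does the sample size sentence reveal a primary outcome?** No. A total of 26 reproduces with a point-biserial correlation of 0.5 (power 80.6%). It also reproduces with a two-group repeated-measures ANOVA at f = 0.5, using two measurements correlated 0.5. A two-group standardised difference of 0.5 would need 128. None of these identifies an outcome, and the planned 0.5 cannot be read as a shift in SD units.

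**The case against.** The strongest reply is that the protocol seems to use pulmonary function as an umbrella for all three measures, and that no sentence says a CAT result alone would be claimed as a lung function effect. That is fair: the documents permit such a claim but do not announce one. Patients can hardly be blinded to blowing through a bottle, and nothing here asks for that.

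PEFR is also not a clean refuge. It depends on effort by patients who know their arm, and the documents do not say whether it was read blind. This objection stands.

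A reader might infer that bias makes the questionnaires far less reliable than PEFR. If an assumed 0.5 SD shift is put on the four questionnaire contrasts only, the chance that at least one of six favours training is 40–68% (correlation 0.8 to 0), against 4–5% for the two PEFR contrasts. The documents do not support that comparison, for three reasons:
- PEFR stays low only because no shift was applied to it. The same 0.5 SD on two independent PEFR contrasts gives 1 − (1 − 0.238)² = 42%.
- With 9 v 4 completers, the any-of-six figure falls to 23–42%.
- The 4–5% counts one direction only. Under the SAP's two-tailed rule it is about 8–10%.

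A reader might also infer that the single-blind label is false. It could correctly describe a blinded data collector or analyst. The documents simply do not say.

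**Conclusion.** The concern holds in a limited form. Knowledge of the arm, the absence of a primary outcome and the single .05 rule are plain in the text. Together they allow an unblinded symptom score to be reported as the intervention effect in a trial aimed at pulmonary function.

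The size that can be defended is the multiplicity alone: about 14–26% for six two-sided tests. This rests on the inferred count of six and an assumed common correlation between 0.8 and 0. With one joint test per outcome it is at most about 14%. Reporting bias would raise these figures by an unknown amount.

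The documents do not show that a biased claim was made or that PEFR is free of bias. The change should be made because it alters which test decides the conclusion and costs little. Confidence is medium.

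**What to change.** In the SAP:
- State that the pulmonary function conclusion rests on PEFR through one test at two-sided .05. This can be a single joint group-by-time GEE test over T1 and T2, or the T1 and T2 contrasts with Holm adjustment (smaller p against .025, then the larger against .05).
- Say whether FEV1 was analysed and, if so, that it is secondary.
- Report CAT and CSSAQ as secondary, open-label symptom outcomes with estimates and 95% confidence intervals, and do not count them as evidence of a pulmonary function effect.
- If any results were known when this is fixed, label the choice post hoc. The protocol text already reports allocation and attrition, so this needs an explicit statement.

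In the protocol and report, note that PEFR depends on effort and may also be affected by knowledge of the arm. Name who was blinded, or drop the single-blind label.

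The cost is one SAP paragraph, intervals from the same GEE models and a sentence or two on blinding, with no new data, visits or staff. The price is that the questionnaire results no longer support the pulmonary function claim, and that the PEFR threshold is slightly stricter if Holm is used.

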**Title: Bubble PEP Training Among Patient
With Chronic Obstructive Pulmonary
Disease in Pulmonary Function Effects**

Statistical Analysis

Principal Investigator : [name]
ClinicalTrials.gov number: NCT04828837

2021/02/25

Statistical Analysis

Statistical analyses were performed using the IBM statistical software SPSS Statistics version 22. The intention-to-treat analysis (ITT) method was employed for data analysis, and the expectation-maximization algorithm (EM) was used to handle missing data. We used t-tests for independent samples, and Fisher's exact tests when more than 20% of cells have expected frequencies <5 or less than 10 observations to examine the homogeneity between groups based on demographic characteristics. Descriptive statistics, including count, percentage, mean, and standard deviation, were used to summarize the data. The intervention effect was evaluated using the generalized estimating equation (GEE) statistical method. Two-tailed tests were conducted, and p-values less than .05 were considered statistically significant.

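### The 80% power is stated for at least 26 patients and an unlabelled effect of 0.5, but only 13 or 14 have day-30 data (the protocol's own figures disagree), where the tests that return 26 have about 50% power

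*Protocol*

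**What the plan says.** The sample-size text is in the Protocol under Design and Participants: "A sample size of at least 26 has 80% power to detect the largest effect size of 0.5". It adds only that G*Power 3.1.9.7 was used with alpha 0.05. It does not give the test, the metric, sidedness, number of measurements, correlation, dropout allowance, or whether 26 is a total or a group size.

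The Protocol's Procedures section reports 13 and 14 patients assigned. It then says "7days follow-up (T1) data were obtained for 17 of the participants" and "1M follow-up (T2) analyses were performed among the 14 participants with complete data". On losses it says "The attrition rates were 30% and 71% for the experimental and control groups, respectively, with an overall attrition rate of 52" per cent.

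The SAP states intention-to-treat, and for missing values "the expectation-maximization algorithm (EM) was used to handle missing data". For the main comparison it says "The intervention effect was evaluated using the generalized estimating equation (GEE) statistical method", without giving model terms. On testing: "Two-tailed tests were conducted, and p-values less than .05 were considered statistically significant". None of this is linked to the sample size.

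**The concern.** Two things are at issue.

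First, an effect size of 0.5 means different things in different G*Power tests. As a standardised mean difference it is half an SD. As a correlation or an f it corresponds to roughly twice that or more. A reader who takes the sentence to promise 80% power for half an SD would read a non-significant result as evidence against a moderate effect. At 13 per group the unadjusted 95% confidence interval is about ±0.81 SD, so that inference would usually be unsafe.

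Second, the 80% belongs to at least 26 patients. About half of the 27 assigned have day-30 data, and the two ways in which the Procedures section reports that number do not agree.

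**Working it through.** **Inputs.** From the documents: N = 26, power 80%, effect size 0.5, alpha 0.05 (Design and Participants); 13 and 14 assigned, 14 with complete T2 data, attrition 30%, 71% and 52% (Procedures); two-tailed tests (SAP). Assumed: 26 is a total, split 13/13. Powers use the noncentral t or F distribution, two-sided.

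**1. Can 26 be reproduced?** Yes.
- Point-biserial correlation r = 0.5: noncentrality √(N·r²/(1−r²)) = √(26 × 0.25/0.75) = 2.94 on 24 df. Power is 80.6%; N = 25 gives 78.9%, so 26 is the exact answer. In SD units, d = 2r/√(1−r²) = 1/√0.75 = 1.155.
- Repeated-measures between-group f = 0.5: noncentrality N·f²·m/(1+(m−1)ρ). With m = 2 and ρ = 0.5 it is 26 × 0.25 × 2/1.5 = 8.67, power 80.6%. With m = 3 and ρ = 0.6 it is 26 × 0.25 × 3/2.2 = 8.86, power 81.5%. The target is d = 2f = 1.0 SD averaged over the measurements. If T0 is one of them and shows no difference, this means 1.5 SD at each follow-up (m = 3) or 2.0 SD (m = 2).

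**2. Does a standardised mean difference of 0.5 return 26?** No. The noncentrality is 0.5/√(1/n₁+1/n₂).

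| Groups | Power at 0.5 SD, unadjusted |
|---|---|
| 13/13 | 23.2% |
| 13/14 | 23.9% |
| 26/26 (if 26 is per group) | 42.4% |
| 64/64 | 80.1% |

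**3. How many patients have T2 data?**
- Intervention: 4 of 13 lost = 30.8%, leaving 9.
- Control: 10 of 14 lost = 71.4%, leaving 4.
- Overall: 14 of 27 lost = 51.9%, leaving 13.
- If 14 had complete data, 13 of 27 were lost = 48.1%, not 52%.

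**4. Power at T2 for the effect that returned 26.** The same formulas at the reduced N:

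| Test | N = 13 | N = 14 |
|---|---|---|
| Point-biserial r = 0.5 | 47.6% | 51.1% |
| Between-group f = 0.5, m = 2, ρ = 0.5 | 47.6% | 51.1% |
| Between-group f = 0.5, m = 3, ρ = 0.6 | 48.4% | 51.9% |

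With the unequal split taken into account, an unadjusted comparison at 1.155 SD has noncentrality 1.155/√(1/9+1/4) = 1.92 and power 41.8% at 9/4. An illustrative 9/5 gives 47.8%.

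**5. What could baseline adjustment recover?** Dividing the residual SD by adjustment, √(1−r²), with 9/4 on 10 df and 1.155 SD: 52% at r = 0.5, 68% at r = 0.7, 82% at r = 0.8. These correlations are assumptions.

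**The case against.** A reader might infer that 26 is an arithmetic error, or that the trial had 23% power. The documents do not support either. The figure reproduces under two standard readings, and calling 0.5 the largest effect size fits a large target better than a moderate one. The 23% applies only if the input was a standardised mean difference, analysed without adjustment.

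The 1.0 to 1.15 SD range is not exhaustive either. A group-by-time test with a partial (SPSS-type) f of 0.5 and three measurements needs 24, or 26 with an assumed nonsphericity factor of 0.85 to 0.90. The difference it targets depends on the correlation. With no T0 difference and equal effects at T1 and T2, it is about 1.2 SD at correlation 0.5 and about 0.75 SD at 0.8. The size in SD units must therefore come from the test actually run.

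It can also be said that 27 were assigned, so the target was met at randomisation, and that the SAP specifies intention-to-treat with EM, so completer powers do not describe the planned analysis. Both are fair. But EM does not replace the missing information. Under missing-at-random and in large samples, the variance of the T2 difference falls to about 0.85, 0.71 or 0.62 of the completer value at correlation 0.5, 0.7 or 0.8. It remains about 2.1, 1.7 or 1.5 times the value with all 27.

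Finally, a flat statement that 80% cannot hold at T2 would go too far, since step 5 reaches 82% at correlation 0.8. The documents give no between-visit correlation to rely on. For the CAT the protocol says "the Intraclass Correlation Coefficient (ICC) was 0.8", but does not label it as one, and it concerns one of three measures.

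**Conclusion.** The concern holds in a limited form. The 26 is under-specified, not shown to be wrong, and it is consistent with a large target effect rather than half an SD.

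Two things need correction. The T2 count of 14 cannot be squared with attrition of 30%, 71% and 52%, which leave 13. And the 80% does not describe day 30: with 13 or 14 patients the tests that return 26 have about 48 to 52% power for the same effect, or 42 to 48% for 1.155 SD once the imbalance between groups is counted.

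This rests on 26 being a total, on two-sided testing at 0.05, and on no correlation being available from the documents to support a gain from adjustment or EM. The attrition conflict needs no assumptions.

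**What to change.** 1. Correct either the T2 count or the attrition rates in Procedures so that they agree (13 remaining with 52%, or 14 with 48%, and group rates to match).
2. Restate the power sentence from the stored G*Power inputs, so that 80% refers to 26 patients with data and to a large effect of about 1 SD or more, according to the test run, and not to 0.5 SD. If T0 was counted as a measurement, give the follow-up difference this implies. If the input was a standardised mean difference, replace 80% by about 23% (42% if 26 was per group).
3. State that 80% was not calculated for the number available at day 30, and that power there is about 50% for the same effect unless a stated correlation supports more.
4. Report effects with 95% confidence intervals, and do not read a non-significant result as no effect.

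The cost is a check of the participant flow, a look-up of the software inputs and about a paragraph of rewording. No extra patients are needed. The downside is a less favourable stated power.
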